In addition, Rasch analysis yields a reliability coefficient, which is useful for determining the measurement precision of the measures. Furthermore, another structural equation model will be used to validate the stroke and OT knowledge measures. A CFA will be used to confirm the factor structure of the stroke and OT knowledge measures to establish its construct validity. The three indices (i.e., the RMSEA, CFI, and TLI) will be used to determine model data fit.⁵²⁻⁵⁴

To manage the possible missing data, we will first examine the patterns and frequency to determine why it is missing. If the data is missing systematically, we will exclude the data by "list-wise" deletion. For example, missing data on some particular items may be attributed to privacy issues. On the other hand, for data that is missing at random, we will use a multiple imputation method implemented in the software ConQuest to derive the estimated value of non-response items. These missing data management processes will also be applied on the remaining parts of this project.

Phase 3: Development of a personal computer version of the stroke and OT knowledge measures.

The stroke and OT knowledge measures (the personal computer version) will be developed and administered in 4 steps. First will be *item calibration*: The Rasch-calibrated item banks (every item with a specific "difficulty" parameter) will be used for developing the stroke and OT knowledge measures and the related simulations. Second will be *starting rule and initial function estimation*: We will use the maximum Fisher information (MFI) as the item selection algorithm, and the maximum a posterior (MAP) method to estimate the patient's ability (i.e., level of function or satisfaction). In administering the stroke and OT knowledge measures, the system will present an initial item with a moderate difficulty from the item banks for the participant. The participant's response to that item will give the CAT a basis for making the first tentative estimate of the tested participant's level of knowledge. Third will be *selecting further items*: The computer will select the item with the largest information gain for further testing; and

fourth, *stopping rule*: Excellent reliability (coefficient = 0.95) will serve as the stopping rule for both CATs.

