The patients and caregivers will be invited and will use the system individually. To determine effect on patients and caregivers, respectively, if a patient is recruited, we will not invite his/her caregiver, and vice versa. Both patients and caregivers will be randomly assigned into an experimental group (receiving the computerized knowledge and education system) or a control group (receiving additional rehabilitation) using numbers randomly generated by a computer. Allocation concealment will be applied. All the participants will be tested by the knowledge system at the beginning of the study, 4 weeks after inception of the study, and 3 months after inception of the study. All the testing will be administered by a research assistant who will be unaware of study-group assignment.

Regarding the sample size needed for this study, a difference of 20% on stroke and OT knowledge in favor of the experimental group will be expected. In addition, we expect that about 70% of the participants will complete all assessments. Therefore, about 25 patients and 25 caregivers will be required for each arm of the trial to achieve a sufficient statistical power of 80%.

Protocols for the experimental and control groups:

The patients/caregivers assigned to the experimental group will first receive the computerized adaptive knowledge testing system. They will be then given adaptive educational materials provided by the educational system according to their testing results. The participants will be instructed to read or

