Baseline characteristics will be reported by descriptive statistics (e.g., mean and SD for continuous variables, or frequency tabulations for categorical variables) for each group. Homogeneity of both groups at the baseline (time 1) will be examined using a Student's t test or Mann-Whitney U test where appropriate. If there are between significant differences between both groups, statistical control (e.g., analysis of covariance, ANCOVA) will be applied for further analysis of effectiveness.

The primary analysis of effectiveness (full-analysis set) will consist of a comparison of the change scores between time 2 to time 1 and time 3 to time 2 in stroke and OT knowledge. Analysis of variance (ANOVA) will be used to compare the change scores between groups. The analyses will be adjusted using ANCOVA for any significant differences at baseline. Intention-to-treat analysis will be applied. Alpha level will be set at 0.05. The statistical analyses will be done by use of SPSS (version 16.0).

Phase 5: Developing a patient-centered OT program.

We will develop a patient-centered, individual tailored OT program on the basis of both a theoretical framework and the opinions of clinical experts. We will employ Steward et al.'s model³⁰ to develop the patient-centered OT program. The 6 main components of Steward et al.'s model include: (1) exploring both disease and illness experience, (2) understanding the whole person, (3) finding common ground, (4) incorporating prevention and health promotion, (5) being realistic, and (6) enhancing the patient-clinician relationship.³⁰ We will develop detailed procedures for administering all the components, as an individual and as a whole. The computerized adaptive stroke and OT knowledge and education systems will be included in the component of "exploring both disease and illness experience." We will invite 5 occupational therapists with sufficient clinical experience and 2 psychiatrists to review the procedures of the patient-centered, tailored OT program. Their comments will be used to revise the procedures until agreement has been reached.

After the procedures for the patient-centered OT program are developed, we will test the feasibility of the program. We will make revisions where necessary. The clinical experts will be consulted if necessary.

Phase 6: Examining the effectiveness the patient-centered OT program on 100 patients.

Subjects:

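### Phase 4 makes four unranked comparisons its primary analysis in each population under one alpha of 0.05, and one of them mainly measures retention rather than benefit

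*Protocol*

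**What the plan says.** Protocol, section (E), Phase 4, Data analysis: "The primary analysis of effectiveness (full-analysis set) will consist of a comparison of the change scores". The sentence specifies this as a "comparison of the change scores between time 2 to time 1 and time 3 to time 2 in stroke and OT knowledge", that is, two intervals for each of two scores. The test is stated as "Analysis of variance (ANOVA) will be used to compare the change scores between groups", moving to ANCOVA if the arms differ significantly at baseline, and "Alpha level will be set at 0.05".

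Stroke and OT knowledge are two separate instruments. Under Phase 3 each has its own adaptive test: "Excellent reliability (coefficient = 0.95) will serve as the stopping rule for both CATs".

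Phase 4, Procedure, treats patients and caregivers as separate questions with unrelated people: "To determine effect on patients and caregivers, respectively, if a patient is recruited, we will not invite his/her caregiver, and vice versa". It gives a sample size for each, 25 per arm, with 70% expected to complete all assessments and 80% power. Testing is at baseline (time 1), 4 weeks (time 2) and 3 months (time 3). The description of the experimental and control procedures expects the education to take about 2 to 3 weeks.

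**The concern.** Phase 4 is a randomised trial with its own sample size, power statement and alpha, and nothing in the text calls it exploratory. Its primary analysis nevertheless consists of several comparisons of equal rank, and the protocol does not say how they combine into a conclusion. A favourable result on one score over one interval could then be presented as a positive primary analysis, and 5% would not describe the error rate of that conclusion.

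The choice of contrasts raises a second problem that no alpha adjustment cures. The second interval starts about when the education stops. An education programme that works and then partly fades would look worse than control on that contrast.

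**Working it through.** **Inputs.** From the protocol: two intervals, two scores, alpha 0.05 (Phase 4, Data analysis); two populations analysed separately, 25 per arm, 70% completion, assessments at baseline, 4 weeks and 3 months (Phase 4, Procedure); education lasting 2 to 3 weeks (Phase 4, group protocols). The protocol gives no correlations, so those below are assumptions.

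**The plan's own sample size.** The figure of 25 per arm cannot be reproduced, because the 20% difference is not defined on a scale and no SD is given. One reading that fits is a 20-point difference with an assumed SD of 20.5, two-sided 0.05 and 80% power: 17 completers per arm, and 17 / 0.70 = 24.3, rounded up to 25. That is one test at the full 0.05, with no visible allowance for several tests. The missing SD does not affect the point made here.

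**Count of tests.** 2 intervals x 2 scores = 4 per population. If scores were kept by domain, as the Phase 2 analysis text suggests, the count would be higher. The number of domains is not stated, so 4 is used.

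**Family-wise error within one population, if any one significant test counts.**

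- Independent tests, two-sided: 1 - 0.95^4 = 0.185.
- Independent tests, results favouring the experimental arm only (0.025 per test): 1 - 0.975^4 = 0.096.

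**Allowing for correlation.** Successive changes share time 2 with opposite sign. With equal variance s² and equal correlation r between the three times, the covariance of the two changes is -(1 - r)s² and each variance is 2(1 - r)s², so their correlation is -0.5 whatever r is. The correlation between the stroke and OT scores is varied from 0.3 to 0.8. One million draws of four correlated normal test statistics under the null gave:

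| Correlation between scores | Any test significant, two-sided | Any test favouring experimental arm |
|---|---|---|
| 0.3 | 16.9% | 9.5% |
| 0.5 | 16.2% | 9.0% |
| 0.8 | 14.0% | 7.8% |

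So the two-sided rate is about 14-17%, and the rate in favour of the experimental arm is about 8-10% against a nominal 2.5%.

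**What the second contrast measures.** Let D2 and D3 be the between-arm differences in mean knowledge at times 2 and 3, with none at time 1 because of randomisation.

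- Time 2 minus time 1 estimates D2.
- Time 3 minus time 2 estimates D3 - D2.
- Time 3 minus time 1 estimates D3.

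Whenever 0 < D3 < D2, the second primary contrast is negative, although the experimental arm is still ahead at 3 months. D3, the remaining benefit, is the sum of the two primary contrasts, but no primary test addresses it. With education over by about week 3 and time 2 at week 4, D3 - D2 is essentially retention.

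**Cost of an adjustment.** Completers per arm: 0.70 x 25 = 17.5. For a two-sample t test, the difference detectable at 80% power (in SD, from the noncentral t) is 0.976 at alpha 0.05 and 1.084 at alpha 0.025.

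**The case against.** Several points on the other side are sound, and they limit the claim.

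- **The success rule is not in the text.** A reader might infer that any single significant result would count. The protocol does not say so. Its sample size paragraph speaks of a difference on stroke and OT knowledge together, which could be read as needing both. Under an all-must-succeed rule there is no inflation. The rates above are therefore conditional.
- **Eight tests are not one family.** A reader might pool patients and caregivers and quote a still larger rate. The protocol asks about them separately ("To determine effect on patients and caregivers, respectively"), in unrelated people with separate sample sizes. No cross-population rate is claimed.
- **The two-sided rate is not the rate of false claims of benefit.** It counts results in favour of control, which nobody would report as effectiveness. The figure for false claims of benefit is 8-10%, to be set against 2.5%.
- **Nothing later is stated to depend on it.** A reader might suppose that a chance finding in Phase 4 would trigger Phase 6. The protocol makes neither Phase 5 nor Phase 6 conditional on a significant Phase 4 result, and Phase 6 has its own randomised comparison.
- **A SAP could settle it.** Ranking and adjustment often sit there. But the protocol is not merely silent here. It states what the primary analysis consists of, and that is four equal comparisons under one alpha. A SAP that named one contrast would be changing that statement.

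The retention argument is separate from multiplicity. Fading works against the experimental arm, so it adds nothing to the false-positive case, but it stands on its own.

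**Conclusion.** The point holds within each population. The Phase 4 primary analysis is four unranked tests with an unallocated alpha of 0.05. If any one is allowed to carry the conclusion, the two-sided error is 18.5% under independence and about 14-17% under the assumed correlations (-0.5 between successive changes, 0.3-0.8 between scores). The chance of a spurious result in favour of the experimental arm is about 8-10%, roughly three to four times the nominal 2.5%. These figures rest on a success rule that the protocol neither states nor excludes.

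The contrast problem needs no such assumption. Time 3 minus time 2 is a poor primary measure of effectiveness for an education that ends before time 2, and the benefit from baseline to 3 months is missing from the primary analysis. Both matters should be corrected, and wording is enough.

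**What to change.** In the Phase 4 Data analysis text, for patients and for caregivers separately:

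1. Name one primary contrast from baseline. Time 2 minus time 1 is the natural choice, because that interval spans the education.
2. Test stroke and OT knowledge on it with Holm at a total two-sided 0.05. Alternatively, state that both must be significant at 0.05.
3. Report time 3 minus time 1 and time 3 minus time 2 as secondary, with confidence intervals, and describe the latter as retention.

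The cost is precision, not recruitment or visits. At the first Holm step the difference detectable with 80% power rises from about 0.98 to 1.08 SD with 17-18 completers per arm. The both-must-succeed option keeps 0.05 for each score but lowers the power to win: with 80% on each, joint power is 0.80 x 0.80 = 64% if the scores were independent, rising towards 80% as they become more correlated.

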The reasons for recruiting 400 patients are described as follows, although a theory-based mathematical function to calculate sample sizes needed for IRT is largely lacking.⁴⁸ First, because of the endurance/acceptability of patients, each patient will be administered about 100 knowledge items randomly selected from the 200 items and their corresponding educational materials. In addition, at least 200 responses for each item, or responses from 200 patients, are strongly recommended for data analysis.^{49, 50} Thus, about 400 patients will be interviewed.

To ensure selection of patients with a broad range of severity and days after stroke onset, we will use a stratified sampling method. Two stratifying variables will be considered. One is stroke severity (using the National Institutes of Health Stroke Scale [NIHSS]⁵¹ as 4 strata: mild [NIHSS 0-5], moderate [6-10], severe [11-20], and very severe [>20]). The other is time after stroke onset (3 strata: 0-3 months, 3-12 months, and > 12 months). We will determine whether the patients cover the entire spectrum of stroke severity and days after onset after one year of data collection. If not, we will later recruit patients who are less representative to ensure adequate representation of the stroke population.

Procedures:

All 200 items and their corresponding educational materials developed in Phase 1 will be coded and saved in personal computers (PC, a touchscreen notebook). We will randomly select items from the item pools to administer on each patient or caregiver. On average, each patient will be tested with about 100 items by face-to-face interview. After the testing, if a participant fails on some items, the corresponding educational materials will be presented. However, each session will be shorter than 1.5 hours to prevent patient/caregiver discomfort and fatigue. The patients/caregivers will be able to take a rest during the testing, if necessary. If a patient/caregiver cannot complete more than 60 items in one session, the patient will be invited to be tested again on another day, but within a week.

The data collection will be carried out by research assistants (full-time or part-time; occupational therapists or research nurses). All items will be administered by face-to-face interview. To avoid any possible interference during the interviews, all the interviews will be administered in a quiet room (e.g., individual treatment room or counseling room).

Data analysis

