We will determine the efficiency (number of items needed) of the stopping rule for the CAT-PROS via a simulation study. We will use the actual data of the stroke patients participating in the item pool testing (phase 2) for simulation. The personal-computer-based version will be developed in a later stage by our information technology personnel.

At this stage, we anticipate that the CATs for stroke and OT knowledge could reach an overall reliability above 0.95 (i.e., excellent reliability) and require less than 10 minutes to administer, or test fewer than 20 items, to ensure its efficiency.

Phase 4: Examining the effectiveness of the computerized adaptive knowledge and education system.

Subjects:

A total of 50 sub-acute patients and 50 caregivers will be recruited from the National Taiwan University Hospital. To cover all possible patients receiving rehabilitation, half of the patients/caregivers will be recruited from inpatients and the other half from outpatients. The patients will meet the following criteria: (1) diagnosis (International Classification of Diseases, ninth revision, clinical modification [ICD-9] codes) of cerebral hemorrhage (ICD-9, 431) or cerebral infarction (ICD 9, 434), (2) ability to follow instructions and complete the computerized knowledge and education system with or without the help of a research assistant, and (3) ability to give informed consent personally. We will exclude patients with other major diseases affecting premorbid ADL independence and mobility (e.g., late stage of Parkinsonism, severe rheumatologic arthritis) and patients with cognitive impairment (MMSE scores < 20).

The 50 caregivers will meet the following criteria: (1) aged 20 or above, (2) having taken care of a stroke patient for more than 1 month, (3) ability to follow instructions and complete the computerized knowledge and education system with or without the help of a research assistant.

Procedure:

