100 sub-acute patients (including inpatients and outpatients) will be recruited from the National Taiwan University Hospital. The patients will meet the criteria (both inclusion and exclusion criteria) mentioned in the phase 4 study. Their caregivers will also be invited to participate.

Power analysis

A difference of 2 points (about 10%) on the Barthel index in favor of the experimental group will be regarded as clinically relevant.⁵⁷ In addition, we expect that about 70% of the participants will complete all assessments. Therefore, about 50 patients will be required for each arm of the trial to achieve a sufficient statistical power of 80%.

Procedure:

The patients will be randomly assigned into an experimental group (receiving the patient-centered program) or a control group (receiving additional rehabilitation). Allocation concealment will be applied. All participants will be assessed by trained raters at the beginning of the study, 4 weeks after inception of the study, 3 months after inception of the study, and 1 year after inception of the study. The raters will be unaware of study-group assignment. The cost of each group will be recorded.

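### Phases 4 and 6 are labelled 'sub-acute' but no listed criterion concerns time since stroke, and the Phase 6 ADL analysis would adjust for onset time only if the arms happened to differ significantly on it

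*Protocol*

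**What the plan says.** Both randomised phases name the same kind of patient. Phase 4, Subjects: "A total of 50 sub-acute patients and 50 caregivers will be recruited from the National Taiwan University Hospital". Phase 6, Subjects: "100 sub-acute patients (including inpatients and outpatients) will be recruited". The protocol gives no definition of 'sub-acute'.

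Phase 6 lists no criteria of its own: "The patients will meet the criteria (both inclusion and exclusion criteria) mentioned in the phase 4 study". The Phase 4 inclusion criteria are an ICD-9 diagnosis of cerebral haemorrhage or infarction, the ability to follow instructions and complete the computerised system, and personal consent. The exclusions are other major disease affecting premorbid function and an MMSE score below 20.

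Phase 4 also explains its recruitment split: "To cover all possible patients receiving rehabilitation, half of the patients/caregivers will be recruited from inpatients and the other half from outpatients".

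Time since onset is given categories in one place only, the stratified sampling for Phase 2: "The other is time after stroke onset (3 strata: 0-3 months, 3-12 months, and > 12 months".

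The Phase 6 Data analysis section compares change scores between groups by ANOVA, from time 1 to time 2 and from time 2 to time 3. It tests baseline homogeneity and moves to ANCOVA only for variables that differ significantly. Alpha is 0.05. The Phase 6 power statement assumes a difference of 2 Barthel points, 70% completion, about 50 patients per arm and 80% power. It gives no SD.

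**The concern.** The protocol names a population without a rule that selects it. A recruiter who works through the listed criteria finds nothing on time since stroke, and the word 'sub-acute' offers no cut-off to apply. Two recruiters could enrol different populations and both be following the text. The result would then be reported for sub-acute patients whether or not that is who was enrolled.

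This matters more in Phase 6 than in Phase 4, because the Phase 6 outcome is change in ADL over short windows. How much a patient changes over those weeks is likely to depend on how far recovery has already gone. The design treats onset time as important enough to stratify on in Phase 2, but the Phase 6 text uses it in neither the criteria nor the described randomisation. It could enter the analysis only through the significance-triggered rule. A strong prognostic variable can be unevenly spread between arms without reaching significance, and even when balanced it adds variance that adjustment could remove.

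**Working it through.** **1. Label against criteria.**

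| Item in Phase 4, reused in Phase 6 | Concerns time since stroke? |
|---|---|
| Diagnosis, ICD-9 431 or 434 | No |
| Able to follow instructions and complete the system | No |
| Able to consent personally | No |
| Excluded: other major disease | No |
| Excluded: MMSE below 20 | No |

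A patient in the longest Phase 2 onset stratum can satisfy all five. Only the undefined label stands against enrolment.

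**2. How often the adjustment rule would act.** Suppose onset time is among the baseline characteristics tested (the protocol neither names nor excludes it) and the test is at 0.05. Under randomisation it is significant in about 5% of trials, so it stays out of the model in about 1 − 0.05 = 95%.

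**3. The plan's own power figure.** It cannot be reproduced directly because no SD is given, but it can be inverted. Completers per arm: 50 × 0.70 = 35. For a two-sample t test, two-sided 0.05 (assumed; sidedness is not stated), 80% power needs d = 0.6794, so SD = 2 / 0.6794 = 2.94. The normal approximation gives 2.99. The stated 50 per arm is thus attainable if the SD of change is about 3 points, but this cannot be verified.

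**4. An illustration in which power falls.** Assume that 2.94 is the SD within one recovery stage, that a share p of entrants is past natural recovery and changes D points less on average, and that both stages have the same SD and the same 2-point benefit. Then

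variance = 2.94² + p(1 − p)D².

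Example, p = 0.3 and D = 4: 8.67 + 0.21 × 16 = 12.03, so SD = 3.47 and power is 66%.

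| p | D = 2 | D = 4 | D = 6 |
|---|---|---|---|
| 0.2 | 77% | 69% | 58% |
| 0.3 | 76% | 66% | 53% |
| 0.5 | 76% | 64% | 50% |

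The SD runs from 3.05 to 4.20.

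**5. The same calculation with one assumption changed.** Let the stable patients have half the SD:

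variance = (1 − p) × 2.94² + p × (2.94/2)² + p(1 − p)D².

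With D = 2, power is 83%, 85% and 90% at p = 0.2, 0.3 and 0.5, a gain over 80%. With D = 4 it is 74% to 77%, and with D = 6 it is 58% to 62%.

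**6. A different mechanism.** Suppose instead that long-standing patients gain nothing from the programme. A 25% share dilutes 2 points to 0.75 × 2 = 1.5, and power with 35 per arm is 56% (normal approximation, SD 2.99).

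Steps 4 to 6 show that both the sign and the size of any change in power depend on p, D, the SD ratio and the benefit by stage. The protocol states none of these.

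**The case against.** **The label has some force.** Both phases state it as the recruited population, and the listed criteria apply on top of it. A reader might infer that the design admits chronic patients. The text does not go that far: such a patient meets every listed criterion yet still falls outside the word 'sub-acute' as commonly understood. What stands is that the word has no boundary, so the restriction cannot be applied consistently.

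**The coverage sentence is weaker evidence than it looks.** The aim of covering all possible rehabilitation patients appears in Phase 4, where the outcome is knowledge, and it explains the inpatient/outpatient split. It can be read as operating within the sub-acute group. Phase 6 imports the criteria, not that sentence. It needs reconciling with the label but does not show an intention to enrol chronic patients in Phase 6.

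**A loss of power is not established.** A reader might infer that the Phase 6 comparison is underpowered because of mixing. The SD is back-solved, and the planning SD may already reflect a mixed intake, in which case the between-stage variance in step 4 is counted twice. D = 6 is about twice that SD and three times the difference that the protocol calls clinically relevant. Also, the Phase 6 primary measures are the FAI, the combined Barthel/FAI score and the adaptive ADL test, so percentages worked in Barthel points do not carry over to them. All of this stands.

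**Covariates often go in a SAP.** That is true of a covariate list, and chance imbalance under concealed randomisation is already allowed for in the test's error rate. But eligibility belongs in the protocol, and the protocol itself fixes the adjustment rule. A rule that adjusts only after a significant baseline test forgoes the precision that a known prognostic variable would give.

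**Conclusion.** The concern holds in two parts. First, 'sub-acute' is not operational in Phase 4 or Phase 6, because it is undefined and no listed criterion concerns time since onset. Second, the Phase 6 analysis fixes an adjustment rule under which onset time would usually be left out, about 95% of the time if tested at 0.05, although ADL change over these windows is likely to depend on it.

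The effect on power is a possibility without a size. The illustrative fall to between 77% and 50% assumes an SD of 2.94, 20% to 50% of entrants past natural recovery, a gap of 2 to 6 points, and equal SD and benefit in both stages. Halving the SD of the stable patients with a 2-point gap turns it into a gain, to between 83% and 90%. Neither range should be quoted as the trial's power.

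The recommendation does not depend on those figures. The population to which the result applies is ambiguous, and a better adjustment rule is available at little cost.

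**What to change.** 1. **Analysis (Phase 6, Data analysis).** Record time since stroke onset at baseline for every patient, from the medical records that the Human Subjects section already says will be used. Enter it as a pre-specified covariate in the Phase 6 ADL analysis, whatever the baseline test shows, in place of the significance-triggered rule. State its form in advance. A linear term costs one degree of freedom; the three Phase 2 categories would cost two. Data extraction is minor. The covariate can recover variance due to recovery stage, but it does not restore an effect diluted by patients who benefit less.

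2. **Population (Phase 4, Subjects, carried into Phase 6).** The sponsor should reconcile the 'sub-acute' label with the listed criteria and with the sentence on covering all rehabilitation patients. Either state the intended onset window among the criteria, or drop the label so that the conclusions describe the patients enrolled. Which of these, and what window, is for the sponsor to decide. A window could slow recruitment if long-standing outpatients were being counted on; dropping the label costs only wording.
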